It is the responsibility of the investigator to maintain accurate and up to date records of all clinical trial related activities, which should be legibly entered onto the CRFs provided. The CRFs should be made available in the event of a formal investigator site audit.

The site will be monitored seven times during the study. This includes both the start-up and the closing visits. Monitoring report will be sent to the project manager for every site inspection.

7.5. Curriculum vitae

All involved researchers participating in the study must show an updated CV documenting their expertise in the relevant clinical field. The CV must be signed and dated by the

physician and a copy must be attached to the protocol if required according to international rules. Another copy should be kept in The Trial Master File and a third copy in the Site File.

7.6. Site File

Meddoc will supply the investigator with a Site File. The Site File should contain all documents relevant for the study. The investigator is responsible to keep the Site File updated and secure that all required documents are present in the File. The Site File will be inspected during the monitor visits.

VII. Consideration

8.1: Consideration of steering committee

The study will be carried out according to the Helsinki declaration with latest amendments, Good Clinical Practice (GCP) and International Ethical Guidelines for Health-related Research Involving Humans (CIOMS guidelines). The participants are active cross-country skiers and will only be included in this clinical trial after approval of the trial by the regional Ethical Committee (REK) and after the XCS have received oral and written information and signed informed consent.

The product to be used in this trial is Jarlsberg cheese commercially available in Norway. To the best of our knowledge, no AE is reported except from person with intolerance of milk and milk product. It is known that vitamin K_2 passing a certain daily dose may increase and strengthen the bone tightness and may therefore have a prophylactic effect on bone fracture. This occurs frequently among active cross-country skiers. Jarlsberg cheese is shown to be one of the Norwegian produced cheeses with the highest level of vitamin K_2 .

In a previously conducted dose-response study on cross country skiers we found the optimal efficacy dose (OED) to increase the osteocalcin levels. Our hypothesis is that this effect is caused by the fermentation of lactic acid to propionic acid by the Propionibacterium freudenreichii in the Jarlsberg Cheese, producing MK 9-4H K2 vitamer and DHNA. The first aim of this study is to compare the effects with the effect of Norvegia Cheese that does not contain MK 9-4H and DHNA to verify the hypothesis. Our second aim is to study the development of BTM, BMD, muscular strength and peak VO2 by the OED of Jarlsberg Cheese, to verify if the cheese could be recommended as prophylactical to prohibit LEA-related conditions.

All participants invited to this clinical trial are entitled to make their decision based on the fullest amount of information available at that time. In order to make the choice, they will be given a written document expressed in a clear concise language of their native tongue to consider. The document will tell potential participants about the aim of the study. Additionally, that blood sampling will be performed between five and eight times in connection with clinical examinations during the two study parts.

Summary: All the included volunteers will receive the daily intake of cheese and clinical examinations free of charge and receive a modest compensation for participation. All participants will be given oral and written information and have to give their written consent to participate in the study. To the best of our knowledge, this study fulfils the entire international requirement to an ethical controlled clinical trial.

8.2: Approval of the project

This study will be performed in Norway and the study protocol together and other requested information will be sent for approval by Regional Ethical Committee (REK). Inclusion of participants will not be started before the approval is received.

The database and storage will be in Norway and must be approved by the Data Register in Norway.

8.3: Informed consent

Before the start of the trial, the investigator will explain the confidentiality of participation in this research project, the objectives of the trial, the specific requirements for the participating

XCS, the trial design and the consequences of participation. Additionally, the investigator has to obtain written informed consent from the participants before inclusion in the study.

8.4: Protection of personal data

The monitor may know the identity of the participants during verification of the source data. However, the monitor has unconditional professional secrecy.

All participant-related material leaving the trial site will be anonymous so that the volunteer only can be identified by date of birth, initials and XCS study identification number. The investigator is responsible for keeping a list with the full names, their citizens' number, and corresponding study numbers according to the demands in GCP.

The participants will receive all the Jarlsberg cheese in the study for free. Additionally, they will get the clinical examination for free and receive a moderate economical compensation. In case they get extra transportation costs for the participation, this will be covered by the study.

IX. Data Management

9.1: Electronical Case Record Forms (eCRF)

The validated electronical data management system InCRF will be used for collecting the data. Mainly the data will be entered on eCRFs by the responsible investigator at stage. Prior to study start; a data entry instruction document will be made. In this study a copy of source data will be collected on a paper. Source data consist of both printouts from the laboratory. In case of printing CRF data from InCRF instead of using paper CRF, it is important that also these are stored. The printed CRF data need investigator's signature and date.

9.2: Study Database

The validated data management system InCRF will be used for collecting the CRF data. The system selected is compliant with GCP guidelines and subject to 21 CFR (Code of federal regulations) FDA part 11 requirements. The final database will be stored in the Statistical Analysis system (SAS ver. 9.4 or later).

9.3: Data handling

The DM will perform the data checks. Once all the errors or issues are corrected or resolved, the investigator shall sign all the eCRFs to acknowledge all the data in the database has reviewed and corrected. After all the eCRFs has electronically signed by the investigator, the Study Statistician will perform final SAS checks and proof reading of safety listing. Thereafter, the database can perform final database hard lock.

The database will be transformed to a labelled SAS database, which also will be locked to prevent all possible changes or additions. In this copy, the responsible statistician can make derivations but no corrections of the data. If corrections are needed, the main basic study database must be re-opened and corrected. The international procedure for such changes will be followed.

X: Discontinuation of treatment

A XCS may discontinue from the study at any time if in the view of the Investigator it is in the participant best interests. Alternatively, the XCS has the right to discontinue the consent and exit the study without prejudice regarding his/her future treatment or care. If a XCS doesn't show up to an agreed visit the investigator should try to motivate the XCS to continue.

10.1: Discontinuation not related to the study question

XCS discontinues the study of administrative reasons or reasons documented not related to the trial treatment will be classified as "Drop out" and replaced by new XCS. The dropouts will be described specially in the statistical analysis.

10.2: Discontinuation related to the study question

XCS discontinues the study of reasons related or might be related to the trial treatment will be classified as "Withdrawal". These will not be replaced by new XCS but included in both the Per-Protocol (PP) and the ITT analysis using the procedure "Last observations carried forward" (LOCF).

XI Statistical Model

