Inclusion of the first participant	17th April 2023
Inclusion of the last participant	28 th April 2023
Last participant finalized comparative study part	23 rd June 2023
Last patient finalized follow-up part	14 th Oct 2023

1.10: Flow Chart

	Сог	nparison pa	rt I	Comparis	son part II
	Week 0	Week 4	Week 8	Week 16	Week 24
Jarlsberg cheese group	Х		Х	х	Х
Norvegia cheese group	Х		Х	Х	Х
Inclusion / Exclusion	Х				
criteria.					
Patient factors	X				
history of disease					
Concomitant treatment	Х	Х	Х	Х	X
Diet registration	Х		Х	Х	X
Vital signs	Х				X
- Blood pressure	Х				X
- Pulse rate	Х				Х
- Body weight	Х				X
Blood sampling					
Bone specific markers	Х	Х	Х	Х	X
Osteocalcin-Vitamin K	Х	Х	Х	Х	X
-HbA1C & Lipids	Х				X
-Vitamin D	Х				X
Sex Hormones	Х		Х	Х	Х
-Haematological	Х				Х
-Biochemical	Х		Х	Х	Х
DXA; BMD, TBS, RMR	Х				Х
LM, MS & Peak VO2	Х				Х
Physical training	Х		Х	Х	X
Menstruation status					Х
Adverse Events [CTCAE]	X	X	Х	Х	Х
Cheese compliance		Х	х	х	Х
End-of-study					Х

II: Introduction

2.1: Background

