Osteoporosis represents substantial health related- and social challenges. Although bone loss is most common among women and elderly persons of both genders, it also affects the younger generation. Young athletes are frequently exposed to microfractures, and the syndrome of Relative Energy Deficiency in Sport (RED-S) with or without disordered eating, is as mentioned a widespread problem among athletes in weight-dependent sports such as

running and cross country skiing^{3,21}. The syndrome causes impairment of metabolic rate, menstrual function, bone health, immunity, protein synthesis and cardiovascular health. The aetiological factor of this syndrome is low energy availability². Our results, supported by other international studies²²⁻²⁶, strongly indicate that the compounds of Jarlsberg cheese may have a promising prophylactic effect on reduced BMD and might affect lipid levels and glucose metabolism. Osteocalcin is showed to build strong bones by increasing the BMD, improve muscular strength, stimulate testosterone production; it has a beneficial effect on cardiac health, lipid pattern and adopositas²²⁻²⁶. Daily intake of Jarlsberg cheese may have a general positive impact on young athletes by protecting against different diseases due to the contents of DHNA and vitamin K₂. DHNA is showed to increase trabecular thickness in ovariectomized mice¹⁷. Cheese has not been regarded as a particularly healthy food because of the contents of milk fat. For young athletes, however the extra energy supply by the cheese is a positive factor in the face of LEA. We do not yet know if the Jarlsberg® Cheese could be used as a food supply to improve bone health, and we do not know if it could help young athletes to maintain or improve bone health.

Since young XCS are at risk for LEA and RED-S, we want to perform studies on XCS athletes.

Recently a dose response study on XCS was performed, and OED for female athletes was estimated to 70 grams of Jarlsberg ® Cheese, and 80 grams for male athletes to increase the tOC and cOC²⁷. The effect of this OED should be tested. All previous studies show a significant decrease in serum magnesium and calcium, and a significant increase of serum urea and serum phosphate. The increase in BMD is not significant, but the increase in RMR is.

2.2: Osteocalcin and Vitamin K

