3.2.2: Exclusion criteria.

Active XCS fulfils at least one of the following criteria will be excluded from participation in the study:

- Eating disorder
- Pregnancy
- Known gastrointestinal disorder.
- Abnormal liver or kidney function.
- Diabetes
- Suffering from verified cancer.
- Under systemic treatment with corticosteroids or other immunosuppressive drugs the last 3 weeks before start of the trial treatment.
- Participating in another clinical trial with pharmaceuticals the last six weeks before start of this trial treatment.
- Known milk product allergy.
- Suffering from diseases or injuries that disable them to perform VO2 or muscular strength tests.
- Not able to understand information.
- Do not want or not able to give written consent to participate in the study.

3.3: Recruitment of athletes

The active XCS will be recruited by the primary investigators team and by advertising in social media. They will be recruited from high schools of sports, and cross-country teams and clubs in the area around Oslo. Active XCS fulfils the inclusion and avoid the exclusion criteria will be asked to participate and to give written consent for participation.

IV: Design and randomization

4.1: Study design

The study is performed as an open randomized stratified parallel group design with two strata²⁸. Sex is used as a stratification factor. The two equal sized strata are chosen because of different Optimal Effective Dose (OED) of cheese for women and men, and because the dose-response study previously performed has shown different response in men and women²⁹.

Within each stratum the participants will be allocated into two treatment groups by block randomisation.

4.2: Randomization

The athletes will be randomized (1:1) to either daily intake of Jarlsberg cheese or Norvegia cheese by using block randomization with random block size between 2 and 6^{29} . The daily amount of cheese will be equal in the two cheese-groups with 5 slices (75g) for females and 6 slices (90g) for males.

14.3: Power Analysis

With a significant level of 5%, a power of 90% and a clinically relevant difference in total osteocalcin increase of one-time SD between the two groups, at least 24 XCSs in each group must be included. By correcting for dropouts during the first part of the study, 30 XCS will be included in each group. Totally 60 XCSs will be recruited for participation²⁹.

4.4: Identification of subjects

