All the XCS will be given one study identification number of four digits constructed as
follows:Digit 1:Indicate the gender study arm (1=female, 2=male)Digit 2&3:Indicate the athlete number consecutively within each sex arm
(01,02,03 etc.)

V: Evaluation

5.1: Osteocalcin and vitamin K

The main response variable in both the first part of the two sex arms in the study will be tOC, the bone specific markers procollagen (PINP), Collagen (CTX1), Bone specific Alkaline Phosphatase (BALP) and parathyroid hormone (PTH). In the second part of the study, Bone mineral density (BMD) will be the most central variable in addition to Resting metabolic rate (RMR), Muscle strength and peak VO₂. The Osteocalcin ratio R_0 , vitamin K_2 including the different vitamers MK 7, 8, 9 and 9/4H and vitamin K_1 will be used as secondary variables in both study parts.

5.2: Bone specific markers

The bone specific markers investigated in the study are Procollagen (PINP), Collagen (CTX1), Bone specific Alkaline Phosphatase (BALP), Parathyroid hormone (PTH).

5.3: Bone mineral density (BMD)

Participants will be weighed in their underwear, and height will be measured with a fixed stadiometer (Seca scale, Mod: 8777021094, S/N: 587728124885, Seca Deutschland, Hamburg, Germany). A dual energy X-ray absorptiometry (Lunar iDXA, E'CORE Software, version 14.10.022; GE Healthcare, Madison, WI) performing a three-site scan (lumbar area [L2-L4]; femoral neck, trochanter, and shaft [proximal femur]; and whole body compares the bone density with the bone density expected for a healthy adult of the same age, sex and ethnicity as the patient. Total body composition for different necessary measures will be performed. The difference is calculated as a standard deviation (SD) score. The difference between the patient measurement and that of a young healthy adult is known as a T score. The T scores classify as follows:

- above -1 SD is normal.
- between -1 and -2.5 SD is defined as mildly reduced bone mineral density (BMD) compared with peak bone mass (PBM)
- below -2.5 SD is defined as $osteoporosis^{30}$.

The difference between the participants measurement and that of someone of the same age and gender is known as a Z score. A Z-score below -2 indicate a bone density lower than it should be for someone of the participant's age. A Z-score is supposed to be 0, above 0 is very good, below -1 is poor. Z-Score < -1 is recommended further follow-up and clinical examination of secondary risk factors³¹.

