Trabecular Bone Score (TBS) will be calculated from the lumbar spine images using TBS iNsight software (Medimaps, Geneva, Switzerland) version 3.0.1. As there is no reference population for TBS in individuals < 40 years, only the absolute values will be used.

Evaluation of the microarchitecture of either tibia or femur neck would give even better information about the bone health of the athletes, and we are looking for possibilities³².

Bodyfat (BF) investigation will be performed. In addition to BMD and TBS, the body composition variables Lean body mass (LM), Bodyfat (BF) and Fat free mass (FFM), will be measured together with RMR, muscle strength and Peak VO2 before starting the clinical part and at the end of the study.

5.4: Muscle strength

Maximal (1 repetition maximum, 1RM) upper body muscle strength will be evaluated by seated pull-down by use of a Technogym Radiant (Technogym, Gambettola, Italy) apparatus and by half-squat performed in a Smith machine (Technogym 2SC multipower, Gambettola, Italy). Test procedure will be initiated by three sets of exercise-specific warm-up with gradually increasing load (ten repetitions at 40%, six repetitions at 60%, and three repetitions at 80% of expected 1RM). The first attempt will be performed with a load approximately 5% below the expected 1RM. After each successful attempt, the load will be increased by 2–5% until the athlete fails to lift the load after 2–3 consecutive attempts. The rest period between each attempt will be 3–4 min. The movement for seated pull-down will start with the handlebar positioned at the same height as the forehead. The athletes must pull the handlebar down to the hip bone. Elbows must be held slightly lateral to simulate a double-poling pull, and the wire must be parallel to the back support on the bench. For the 1RM to be accepted, the handlebar must be pulled completely down in one continuous motion with hands parallel³³.

For half-squat, at the familiarization session, the correct depth (90° knee angle) will be noted for reproduction. The position of the feet will be marked, and the correct depth controlled with an elastic band^{33,34}.

For additional information about changes in muscle mass during the study, lean body mass (LM) will be extracted from the body composition outcomes obtained from the DXA measurement.

5.5: Peak VO₂

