5.7.3 Bone Turnover markers

Collagen 1 (CTX-1) Procollagen 1 (PINP) Parathyroid hormone (PTH) Bone specific alkaline phosphatase (BALP)

5.7.4 Sex hormones:

Estradiol Progesterone Testosterone LH FSH

5.7.5: Haematology

Haemoglobin (Hgb) HbA₁C

5.8: Diet registration

Diet registration will be performed by the participants. The daily intake of all food will be recorded daily for four days consecutively at screening and every eight weeks during the study. A pre-evaluated questionnaire based "diet.no" will be used and recorded on an electronical diet APP by the participants. The diet registration will be supervised by a qualified monitor. The results will be evaluated by the investigating team.

5.9: Menstruation status

To control the hormone blood sample results to female XCS, this group will be interviewed about their menstruation status. This includes menarche length, cycles day and use of hormonal contraceptives.

5.10: Cheese, supplement, and activity registration

The cheese, supplement of vitamin D and activity will med recorded in a form for daily registration. The activity will be recorded weekly. The parameters to be recorded are low- and high intensity running and roller-ski in hours, and low- and high-load strength exercise. The forms are handed out every fourth week of the study and collected by the investigator or the research assistant.

5.11: Compliance

The participants must eat their daily prescribed dose of cheese and vitamin D, register their activity weekly, and fill in their diet APP 4 days before their control every 8 weeks.

5.12: Adverse Events (AE)

5.12.1: Common Terminology Criteria for Adverse Events version 4.0 (CTCAE)

The CTCAE is divided in 26 System Organ Class (SOC) in accordance with the MedDRA hierarch. Within each SOC, AE are listed and accompanied by descriptions of severity or grade:

- Blood and lymphatic system disorders (11 Items)
- Cardiac disorders (36 Items)
- Congenital, familial, and genetic disorders (1 Items)
- Ear and labyrinth disorders (9 Items)
- Endocrine disorders (11 Items)
- Eye disorders (25 Items)
- Gastrointestinal disorders (117 Items)
- General disorders and administration site conditions (24 Items)
- Hepatobiliary disorder (16 Items)
- Immune system disorders (6 Items)
- Infections and infestations (76 Items)
- Injury, poisoning and procedural complications (78 Items)
- Investigations (38 Items)
- Metabolism and nutrition disorders (24 Items)

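### LOCF for Withdrawals enters exactly zero change for BMD and every other variable measured only at weeks 0 and 24, in both ITT and PP; the harm is small if withdrawals are few and balanced, but its direction cannot be relied on

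*Protocol*

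**What the plan says.** Section 10.2 defines a Withdrawal as someone who leaves for reasons related, or possibly related, to the trial treatment. It continues: "These will not be replaced by new XCS but included in both the Per-Protocol (PP) and the ITT analysis using the procedure" of LOCF. No variable is exempted.

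Section 10.1 defines a Drop out as someone who leaves for administrative or documented unrelated reasons. Drop outs are classified as such "and replaced by new XCS. The dropouts will be described specially in the statistical analysis". No analysis set is named for them. Section 4.1 makes the trial open: "The study is performed as an open randomized stratified parallel group design".

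On timing, section 5.3 says the body-composition variables "will be measured together with RMR, muscle strength and Peak VO2 before starting the clinical part and at the end of the study". The flow chart in 1.10 agrees: the rows for "DXA; BMD, TBS, RMR" and for LM, strength and peak VO2 are marked at weeks 0 and 24 only. Osteocalcin and bone markers are also marked at weeks 4, 8 and 16. No exit DXA, RMR or performance test is planned for people who leave early.

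On importance, section 5.1 says: "In the second part of the study, Bone mineral density (BMD) will be the most central variable", with RMR, strength and peak VO2 named beside it. Section 11.2 plans ANCOVA with a baseline covariate and repeated measurements.

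**The concern.** LOCF replaces an unknown final value with the last one seen. Where the only earlier value is baseline, that amounts to asserting that the person did not change in 24 weeks. The rule reaches all of the second aim and the BMD part of the first.

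Three things are at stake. A true effect can be diluted. If one cheese loses more people than the other, and the variable drifts in both arms over the season, LOCF can create a difference that is not there. And PP, which should show whether the result holds among those who took the cheese as planned, must carry people who left because of it, with the same imputed values as in ITT.

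**Working it through.** **The plan's own figure.** Two-sided 5%, 90% power, difference 1 SD: the normal formula gives 22 per group, the t distribution 23. The stated 24 gives power 0.924, and 24/(1 - 0.20) = 30. So 24 and 30 reproduce. They concern total osteocalcin, and the implied 20% is for dropouts, which 10.1 keeps apart from Withdrawals. They therefore supply no withdrawal rate for the present question.

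**Bias of LOCF on a two-point variable.** Let wJ and wN be the shares of Withdrawals without a week-24 value on Jarlsberg and Norvegia, d the cheese effect, and c the change common to both arms. Withdrawal is taken as unrelated to outcome. The LOCF contrast is

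(1 - wJ)(c + d) - (1 - wN)c = d - wJ x d - (wJ - wN) x c.

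- Target is the effect had all continued (d): bias = -(wJ x d) - (wJ - wN) x c.
- Target is the as-randomised effect, with the effect fully lost after stopping, (1 - wJ)d: bias = -(wJ - wN) x c. This is zero with equal withdrawal.

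**Simulation.** Assumptions: 30 per arm, ANCOVA on baseline, residual SD 1, baseline correlation 0.8, 20,000 trials per scenario. Rates, d and c are assumed, since the protocol gives none.

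*Equal withdrawal, d = 1, target had all continued:*

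| Withdrawal per arm | Effect under LOCF | Power, LOCF v observed data, c = 0 | Same, c = 1 |
|---|---|---|---|
| 5% | 0.95 | 0.954 v 0.957 | 0.930 v 0.955 |
| 10% | 0.90 | 0.937 v 0.944 | 0.889 v 0.946 |
| 20% | 0.80 | 0.890 v 0.912 | 0.781 v 0.916 |

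Type I error stays near 5% when withdrawal is equal.

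*Unequal withdrawal, d = 0:*

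| Jarlsberg v Norvegia | c | Bias = -(wJ - wN) x c | Type I error |
|---|---|---|---|
| 10% v 3% | 1 | -0.07 | 6% |
| 10% v 3% | 2 | -0.14 | 7% to 8% |
| 20% v 5% | 1 | -0.15 | 9% |
| 20% v 5% | 2 | -0.30 | 17% |

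If both arms fall (c = -1), 20% v 5% gives +0.15: a false benefit for Jarlsberg.

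*As-randomised target, effect lost after stopping, d = 1, c = 1:* with equal withdrawal LOCF gives 0.95 / 0.90 / 0.80 at 5% / 10% / 20%, which is the truth, while observed-data ANCOVA gives 1.0. At 10% v 3% LOCF gives 0.83 against a truth of 0.90; at 20% v 5%, 0.65 against 0.80.

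*Informative withdrawal in the Jarlsberg arm* (lower week-24 values leave more often, logistic slope 1; d = 0, c = 0; 40,000 trials): at 5% / 10% / 20% observed-data ANCOVA is off by +0.05 / +0.09 / +0.18 and LOCF by +0.05 / +0.08 / +0.14.

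**Total osteocalcin.** Suppose half of the withdrawals precede week 8 and the week-4 effect is half the week-8 effect. The mean share carried forward is (0 + 0.5)/2 = 0.25, so the week-8 effect is 1 - (w/2)(0.75) = 0.98 at w = 5% and 0.925 at 20%. The distortion is smaller than for BMD.

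**PP.** Section 5.11 tells participants: "The participants must eat their daily prescribed dose of cheese and vitamin D, register their activity weekly". Under 10.2 a Withdrawal has the same imputed value in PP and ITT, so the two sets cannot differ on that person. They can still differ if PP leaves out completers who adhered poorly.

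**Replacement and dates.** Section 6.7 ends the study on 14 October 2023. Minus 168 days, the last possible entry is 29 April, and the stated last inclusion is 28 April. Inclusion opens on 17 April, so the first week-4 visit is 15 May. A replacement within these dates would precede any post-baseline measurement. One entering on 31 May, when recruitment closes, would finish on 15 November, 32 days after the stated end.

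**The case against.** **LOCF may be right for an ITT target.** If the as-randomised effect is wanted, the effect vanishes after stopping and withdrawal is equal, LOCF is unbiased and observed-data ANCOVA overstates. This stands. It requires all three conditions, and the protocol states none of them.

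**Removing LOCF does not make the analysis safe.** Under the informative-withdrawal scenario observed-data ANCOVA is no better and slightly worse. People who leave because of the cheese are those for whom missing-at-random is least secure. With two time points, multiple imputation from the same ANCOVA variables adds essentially nothing. This stands too and shapes the fix.

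**The larger figures need large inputs.** They do: 17% type I error takes 20% v 5% withdrawal and a 2 SD common change. Section 8.1 reports no known adverse events apart from milk intolerance, which suggests few withdrawals. At 5% to 10% balanced and c up to 0.5 SD, LOCF power stays at 0.92 to 0.95 for a 1 SD effect.

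**Background results might seem to show which variable is most at risk.** A reader might infer from section 2.1, "The increase in BMD is not significant, but the increase in RMR is", that RMR is more exposed to the common-change term than BMD. The text does not support that. It reports changes in earlier Jarlsberg studies, which combine c and d, so it cannot identify c for either variable.

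**Set membership belongs in the SAP.** For Drop outs this largely holds. A reader might infer from 10.1 that they are removed from ITT; the section does not say so. LOCF, PP membership of Withdrawals and replacement are, however, fixed in the protocol itself. It is also fair that 5.11 instructs participants and does not define PP, and that leaving the study is not the same as stopping the cheese with follow-up (6.2.3, phase 2).

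**Conclusion.** The point holds and should be fixed. A Withdrawal without a week-24 value contributes zero change for BMD, TBS, LM, RMR, strength and peak VO2; this follows from the rule and the schedule alone.

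The size depends on assumed inputs. With few, balanced withdrawals it is small. It becomes material when withdrawal is unequal and both arms change. The sign then follows c and the imbalance, so LOCF cannot be defended as conservative.

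A reader might conclude that the BMD result will be seriously biased, or that PP becomes meaningless. The documents support neither: no rate, d or c is given, and PP can still leave out completers who adhered poorly, so it is weakened and not emptied. No size is claimed for the replacement of Drop outs.

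**What to change.** 1. Remove LOCF as the primary rule. Analyse osteocalcin and bone markers with a likelihood-based repeated-measures model on all observed visits, in line with 11.2.
2. For variables measured only at weeks 0 and 24, use baseline-adjusted ANCOVA on observed week-24 values, including those of participants who stop the cheese but still attend. State the target effect and the missing-at-random assumption. Add a sensitivity analysis with shifted values for Withdrawals; zero change can be one scenario. Use multiple imputation only if it brings in auxiliary variables.
3. Take imputed Withdrawals out of PP.
4. In 10.1, state that Drop outs stay in ITT with their observed data and that later recruits are newly randomised additions, not substitutes. Reconcile replacement with the dates in 6.7.

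The cost is protocol wording, modest extra analysis and a missing-at-random assumption to defend. Intervals are slightly wider than under LOCF when there is little common change: for a 1 SD effect and c = 0, the standard error is about 0.27 v 0.25 at 10% withdrawal and 0.29 v about 0.245 at 20%. At c = 1 the gap nearly vanishes (0.274 v 0.275, and 0.292 v 0.285).
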